8.7 Efficacy Subgroup Analyses

The following subgroup analyses will be conducted for the primary efficacy endpoint in the ITT_A population. Treatment difference between each upadacitinib treatment group and placebo group with point estimate and 95% confidence interval using normal approximation will be presented. The NRI-C approach will be used for missing data handling. No p-value will be provided for subgroup analysis.

- Sex (male, female)
- Age (\leq median, $>$ median)
- Race (white, non-white)
- Bio-IR status (Bio-IR, Non-Bio-IR)
- Baseline corticosteroid use (yes, no)
- Baseline Adapted Mayo score (≤ 7 , > 7)
- Baseline Full Mayo score (≤ 9 , > 9)
- Prior exposure to anti-TNF (yes, no) for non-Bio-IR
- Prior exposure to biologic therapy (yes, no) for non-Bio-IR
- Baseline weight (\leq median, $>$ median)
- Presence of pancolitis at Baseline (yes, no)
- Disease duration at Baseline (\leq median, $>$ median)
- Baseline hs-CRP (≤ 5 mg/L and > 5 mg/L)
- Region (US versus non-US)
- Baseline aminosalicylate use (yes, no)

For a subgroup with the resulting categories that has fewer than 10% of the planned study size, subgroup analyses will not be presented for that category.

In addition, the following key secondary efficacy endpoints will be analyzed in the Bio-IR and non-Bio-IR subgroups in the ITT_A population.

- The achievement of endoscopic improvement at Week 52;
- The achievement of clinical remission per Adapted Mayo score at Week 52 among subjects who achieved clinical remission at the end of the induction treatment in the Induction Study;
- The achievement of clinical remission per Adapted Mayo score at Week 52 and corticosteroid free for ≥ 90 days immediately preceding Week 52 among subjects who achieved clinical remission at the end of the induction treatment in the Induction Study;
- The achievement of endoscopic improvement at Week 52 among subjects who achieved endoscopic improvement at the end of the induction treatment in the Induction Study;
- The achievement of endoscopic remission at Week 52;
- The achievement of clinical response per Adapted Mayo score at Week 52;
- The achievement of histologic-endoscopic mucosal improvement at Week 52;
- The achievement of mucosal healing at Week 52.

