2.4 Sample Size Determination

The sample size for the Maintenance Study is based on the expected proportion of subjects who achieve clinical remission per Adapted Mayo score at Week 52. The assumptions of clinical remission rates were based on the historical data from other compounds with similar or different MOAs. In vedolizumab Phase 3 UC study, the clinical remission rate was 16% in placebo group and 42% in treatment group.¹ In tofacitinib Phase 3 UC study, the clinical remission rate was 11.1% in placebo group and 40.6% in 10 mg BID treatment group.² Considering the factors that may influence the clinical remission rate (e.g., differences in MOAs, patient population, and clinical remission definition), clinical remission rates are assumed to be 12% in the placebo group and 40% in the upadacitinib treatment group at Week 52.

Assuming clinical remission rate of 12% in the placebo group and 40% in one of the upadacitinib QD treatment groups at Week 52, a sample size of 150 subjects in placebo and 150 subjects in each of the upadacitinib 15 mg QD and 30 mg QD treatment groups will have > 95% power to detect the 28% treatment difference in the primary endpoint between an upadacitinib dose and placebo using two-sided Fisher's exact test at a 0.025 significant level with multiplicity adjustment. Under the assumption that average response rate in upadacitinib doses at the end of induction treatment in the Induction Studies is 50%, a total of approximately 450 subjects will be re-randomized to upadacitinib 15 mg QD or 30 mg QD treatment groups or placebo in a randomization ratio of 1:1:1 if they achieved clinical response from upadacitinib 45 mg QD in the Induction Studies. The assumption of an average response rate of 50% in upadacitinib doses after induction is based on the Phase 2b results.

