2.2 Study Design Overview

This is a Phase 3, multicenter, randomized, double-blind, placebo-controlled study designed to evaluate the efficacy, safety, and pharmacokinetics of upadacitinib as induction therapy in subjects with moderately to severely active UC who have been inadequate responders or intolerant to oral aminosalicylates, immunosuppressants, corticosteroids, and/or biologic therapies.

[figure not shown]
The number of enrolled non-biologic-inadequate responders (non-bio-IR) subjects will be at least 25% and not exceed 50%. Among bio-IR subjects, the Induction Study will allow enrollment of up to 30% of subjects who have failed 3 or more biologics. Among non-bio-IR subjects, it will allow enrollment of up to 20% subjects who could also have previous use of biologic therapy but discontinued based on reasons other than inadequate response, loss of response, or intolerance. Subjects who have used a biologic up to 1 year and have discontinued for reasons other than inadequate response, loss of response, or intolerance (e.g., change of insurance/reimbursement, well-controlled disease, etc.) may be enrolled but must meet other criteria for inadequate response, loss of response, or intolerance to aminosalicylates, corticosteroids, or immunosuppressants as defined in the protocol.

The Induction Study consists of:

1. Screening period of up to a maximum of 35 days;
2. **Part 1:** a randomized, placebo-controlled 8-week double-blind (DB) induction period;
3. **Part 2:** an 8-week open-label (OL) extended treatment period for subjects who do not achieve clinical response at Week 8 of Part 1;
4. 30-day follow-up period.

The schematics of the Induction Study design are shown in [Figure 1](#).

Figure 1. Induction Study Schematic

In Part 1, approximately 462 subjects will be enrolled. Eligible subjects will be randomized in a 2:1 ratio to one of the two treatment groups (DB upadacitinib 45 mg QD or matching placebo) for 8 weeks.

- Group 1: Upadacitinib 45 mg QD (blinded, n = 308)
- Group 2: Placebo QD (blinded, n = 154)

Part 2 is an 8-week OL extended treatment period for subjects who did not achieve clinical response at Week 8 in Part 1. The objectives of Part 2 are to offer upadacitinib induction treatment to placebo clinical non-responders from Part 1, and to evaluate delayed clinical response to upadacitinib in subjects who do not initially respond to upadacitinib during Part 1.

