2.4 Sample Size Determination

For the Induction Study (Part 1), approximately 462 subjects are expected to be randomized to upadacitinib 45 mg QD or placebo in a randomization ratio of 2:1. The sample size for this study is based on the expected proportion of subjects who achieve clinical remission per Adapted Mayo score at Week 8. Based on the results from Phase 2b upadacitinib Study M14-234 (Substudy 1), the proportions of subjects achieving clinical remission per Adapted Mayo score in upadacitinib 45 mg QD group and placebo

group are 19.6% and 0%, respectively. Considering the small sample size in Phase 2b study and more stringent definition of primary endpoint used for Phase 3 studies, clinical remission rate is assumed to be 5% in the placebo group and 18% in the upadacitinib 45 mg QD treatment group. Based on these assumptions, a sample size of 154 subjects in placebo and 308 subjects in upadacitinib dose will have > 95% power to detect the 13% treatment difference in the primary endpoint between upadacitinib 45 mg QD group and placebo group using two-sided Fisher's exact test at a 0.05 significant level.

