8.7 Efficacy Subgroup Analyses

The following subgroup analyses will be conducted for the primary efficacy endpoint in the ITT1 population. Treatment difference between upadacitinib treatment group and placebo group with point estimate and 95% confidence interval using normal approximation will be presented. The NRI-C approach will be used for missing data handling. No p-value will be provided for subgroup analysis.

- Sex (male, female)
- Age (\leq median, $>$ median)
- Race (white, non-white)
- Bio-IR status (Bio-IR, non-Bio-IR)
- Baseline corticosteroid use (yes, no)
- Baseline Adapted Mayo score (≤ 7 , > 7)
- Baseline Full Mayo score (≤ 9 , > 9)
- Prior exposure to anti-TNF (yes, no) for non-Bio-IR
- Prior exposure to biologic therapy (yes, no) for non-Bio-IR
- Baseline weight (\leq median, $>$ median)
- Presence of pancolitis at Baseline (yes, no)
- Disease duration at Baseline (\leq median, $>$ median)

- Baseline hs-CRP (≤ 5 mg/L and > 5 mg/L)
- Region (US versus non-US)

In addition, the following key secondary efficacy endpoints will be analyzed in the Bio-IR and non-Bio-IR subgroups in the ITT1 population.

- Endoscopic remission at Week 8
- Endoscopic improvement at Week 8
- Clinical response per adapted Mayo score at Week 8

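### The normal-approximation subgroup intervals in both Phase 3 SAPs are mis-calibrated in the smallest categories, mainly in Substudy 2, where an empty placebo cell is likely and no size floor applies.

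*SAP*

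**What the plan says.** Section 8.7 of both Phase 3 SAPs gives each subgroup difference in clinical remission a point estimate and a "95% confidence interval using normal approximation will be presented". NRI-C handles missing data and there are no subgroup p-values. Neither section gives a formula, a small-sample alternative or a rule for an empty cell. Protocol 8.1.7 lists the subgroups but sets no interval method. The overall primary analysis (8.4.3 in both SAPs) uses a CMH-based interval instead.

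The Substudy 3 SAP does not present a category with "fewer than 10% of the planned study size". It does not say which planned size it means. The Substudy 2 SAP has no such rule, and its list includes "Prior exposure to biologic therapy (yes, no) for non-Bio-IR" as well as prior anti-TNF exposure within the same stratum.

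Substudy 2 SAP 2.2 sets the enrolment limits. The non-Bio-IR share "will be at least 25% and not exceed 50"%, and within it "it will allow enrollment of up to 20% subjects who could also have previous use of biologic therapy". In Substudy 2 SAP 2.4 the "clinical remission rate is assumed to be 5% in the placebo group", against 18% on upadacitinib, after 0% on placebo in Phase 2b. In Substudy 3 SAP 2.4 "clinical remission rates are assumed to be 12% in the placebo group and 40% in the upadacitinib treatment group at Week 52", with 150 on placebo and "150 subjects in each of the upadacitinib 15 mg QD and 30 mg QD treatment groups".

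**The concern.** The normal approximation for a difference in proportions is least reliable when an arm is small and its rate is near zero. Substudy 2 combines a low planned placebo rate with a category that its own enrolment caps keep small. With no placebo remitters, the estimated placebo variance is zero and the interval treats the placebo rate as known. With no subgroup p-values planned, the interval is the only measure of uncertainty in each row. A small category could then appear to show a clear benefit because of the formula and not because of the data.

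**Working it through.** **The plan's own figures.** The documents state no coverage for these intervals. The planning rates and sizes were checked against the stated power of more than 95%, using exact enumeration of the two-sided Fisher test. Substudy 3 (12% vs 40%, 150 per arm, alpha 0.025) gives 99.97%. Substudy 2 (5% vs 18%, 154 vs 308, alpha 0.05) gives 98.9%. Both agree with the SAPs.

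**Category sizes.**
- Substudy 2, prior-biologic non-Bio-IR: at least 25% and at most 50% of 462 is 115.5 to 231. A cap of 20% gives at most 23.1 to 46.2. One third on placebo is at most 7.7 to 15.4, so about 8 to 15. The 2:1 ratio is a fair assumption here because randomisation is stratified by previous biologic use within non-Bio-IR (Substudy 2 SAP 2.3). The prior anti-TNF category can be no larger. These are upper bounds.
- Substudy 3, smallest category presented: 10% of 450 is 45, or 15 per arm. If the floor refers to the 525 planned for Cohort 1 it is about 17 to 18 per arm, and if to the 750 planned overall, 25 per arm. This assumes 1:1:1 within the category.

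**Interval assumed.** Unpooled Wald: d ± 1.96 × √[p0(1−p0)/n0 + p1(1−p1)/n1], where d = p1 − p0 and 0 denotes placebo. Coverage is the total probability, over all pairs of two independent binomials, of outcomes whose interval contains the true difference. The Newcombe hybrid-score interval is the comparison.

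| Setting | Placebo / active n | Wald coverage | Newcombe coverage |
|---|---|---|---|
| Substudy 2, 5% vs 18% | 8 / 15 | 92.2% | 97.0% |
| Substudy 2, 5% vs 18% | 15 / 31 | 92.8% | 97.4% |
| Substudy 2, 5% vs 18% | 23 / 46 | 94.5% | 96.9% |
| Substudy 2, 5% vs 18% | 77 / 154 | 94.6% | 95.5% |
| Substudy 3, 12% vs 40% | 15 / 15 | 92.8% | 95.5% |
| Substudy 3, 12% vs 40% | 25 / 25 | 94.0% | 95.3% |

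Because the Substudy 2 caps are upper bounds, the category could be smaller still. At 5 / 10 Wald coverage is 87.3%.

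**Empty placebo cell.** The probability is (1 − p0)^n0. At 5%, 0.95^15 = 46.3% and 0.95^8 = 66.3%. In Substudy 3 at 12% and 15 per arm, 0.88^15 = 14.7%.

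**Worked example, 0/15 vs 6/31** (complete data). d = 0.1935.
- Wald: variance = 0 + 0.1935 × 0.8065 / 31 = 0.00503, SE = 0.0710, interval 5.4 to 33.3 points.
- Newcombe: the Wilson limits are 0 to 0.2039 for placebo and 0.0919 to 0.3628 for active. Lower limit = 0.1935 − √[(0.1935 − 0.0919)² + 0.2039²] = −0.034. Upper limit = 0.1935 + (0.3628 − 0.1935) = 0.363. The interval is −3.4 to 36.3 points.

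The Wald interval excludes zero and the Newcombe interval does not.

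**Width.** Mean widths, Wald then Newcombe:
- Substudy 3 at 15 / 15: 0.571 and 0.563.
- Substudy 2 at 15 / 31: 0.332 and 0.415 (+25%).
- Substudy 2 at 8 / 15: 0.444 and 0.606 (+36%).

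**The case against.** The strongest case against is that this is a preference between interval methods for a few descriptive rows. Subgroup results carry no p-value and lie outside the type I error procedures in Section 12.0 of each SAP. At the planning rates the shortfall is 2 to 3 points in the most extreme categories and about 1 point or less from 25 placebo subjects upward. Substudy 3 already suppresses small categories. In Substudy 2 the Newcombe interval replaces under-coverage with over-coverage. All of this stands and limits the weight of the point.

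Two further limits also stand. Neither SAP writes out the formula. The multiple-imputation text in 8.3.1 of the Substudy 3 SAP ends in a redaction, and its version history says that 8.3.1 specifies how the interval for a difference in proportions is derived under NRI-C. The withheld text may deal with zero variance. Still, 8.7 names its own method, which is different from the CMH-based interval. Also, under NRI-C an imputed placebo remitter in any of the 30 datasets makes the placebo variance non-zero.

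A reader might infer three stronger things that the documents do not support:
- That the intervals are too narrow throughout. At the Substudy 3 planning rates and 15 per arm, the Wald interval is on average slightly the wider of the two; its shortfall comes from where it is centred.
- That false-positive subgroup findings are inflated. With both arms at 5% in the 15 / 31 setting, Wald covers 96.6%.
- That coverage falls to around 81%. That needs rates such as 2% vs 10% at 8 / 15, which appear in neither SAP's planning assumptions.

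**Conclusion.** The point holds as a minor one. In the smallest Substudy 2 categories the stated method covers about 92% to 93% at the planned rates, and an empty placebo cell has a 46% to 66% chance at the sizes the enrolment caps allow. In Substudy 3 the shortfall is smaller or similar and depends on an undefined term: 92.8% if the floor means 10% of 450, 94.0% if it means 10% of 750. The primary test, the ranked secondary tests and the type I error control are untouched.

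This rests on three assumptions: that normal approximation means unpooled Wald, that the randomisation ratio holds within each category, and that subgroup rates are near the planning rates. The coverage figures are for complete data and do not model the imputation.

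**What to change.** In 8.7 of both Phase 3 SAPs, name a score-based interval (Newcombe hybrid-score or Miettinen-Nurminen) in place of the normal approximation. State how it is combined over the 30 NRI-C imputations so that between-imputation variance is kept, for example multiple-imputation Wilson limits in each arm followed by the Newcombe combination. Putting the averaged imputed proportions straight into the Newcombe formula would drop that variance and should be avoided.

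Add the Substudy 3 floor of 10% to the Substudy 2 SAP, and define the planned study size in both. In Substudy 2, 10% of 462 is 46.2, which equals the largest size the caps allow for the prior-biologic non-Bio-IR category, so that row would usually be dropped. The score interval then protects the small rows that remain.

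The cost is a few lines in each SAP and some programming for the imputation step. In small Substudy 2 categories the intervals become asymmetric, about 25% to 36% wider at the planning rates, and somewhat conservative at about 97% coverage.

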9.0 Safety Analyses

9.1 General Considerations

Safety analyses will be performed on the safety populations for SA_A population. In addition, safety summaries will be provided on SA_B, SA_C, SA_D and SA_UPA populations.

The standard safety analyses will include reporting of adverse events (AEs), adverse events of special interest (AESIs), laboratory, and vital signs measurements. Frequency tables and exposure adjusted event rate per 100 patient-years tables of subjects with

treatment-emergent adverse events (TEAEs) by system organ class (SOC) and by preferred term (PT) as in the Medical Dictionary for Regulatory Activities (MedDRA) dictionary will be provided by treatment group. All continuous laboratory parameters and vital signs variables at each visit will also be summarized by treatment group. Frequency tables of subjects meeting criteria for potentially clinically significant vital sign values and for potentially clinically significant laboratory values will be provided by treatment group.

The Baseline for the analysis of potentially clinically significant laboratory and vital sign values, and shift tables is the last available measurement before upadacitinib administration in the (Phase 2b) Induction Studies for subjects who received upadacitinib in the Phase 2b or Phase 3 Induction Studies; or the last available measurement before placebo administration in the (Phase 2b) Induction Studies for subjects who only received placebo in the Phase 2b or Phase 3 Induction Studies.

9.2 Adverse Events

Adverse events (AEs) will be summarized and presented using primary MedDRA System Organ Classes (SOCs) and preferred terms (PTs) according to the version of the MedDRA coding dictionary used for the study at the time of database lock. The actual version of the MedDRA coding dictionary used will be noted in the AE tables and in the clinical study report. Specific adverse events will be counted once for each subject for calculating percentages, unless stated otherwise. In addition, if the same adverse event occurs multiple times within a subject, the highest severity and level of relationship to investigational product will be reported.

9.2.1 Treatment-Emergent Adverse Events

The Treatment-Emergent Adverse Events (TEAEs) for SA (SA_A, SA_B, SA_C and SA_D) and SA_UPA populations are defined as follows.

SA (SA_A, SA_B, SA_C and SA_D) population: TEAEs are defined as events that begin either on or after the first dose of the study drug in the Maintenance Study and

- within 30 days after the last dose administration of the study drug for subjects who do not participate in the long-term extension Study M14-533 or
- until first dose of study drug in the Study M14-533 if the subject is enrolled into Study M14-533

SA_UPA population: TEAEs are defined as events that begin either on or after the first dose of upadacitinib study drug in Maintenance Study and

- within 30 days after the last dose administration of the study drug for subjects who do not participate in the long-term extension Study M14-533 or
- until first dose of study drug in the Study M14-533 if the subject is enrolled into Study M14-533

If an incomplete onset date was collected for an adverse event, the event will be assumed to be treatment-emergent unless there is other evidence that confirms that the event was not treatment-emergent (e.g., the event end date was prior to the study drug start date). The number and percentage of subjects experiencing treatment-emergent AEs will be summarized.

9.2.2 Adverse Event Overview

An overview of AEs will be presented consisting of the number and percentage of subjects experiencing at least one event for each of the following AE categories:

- Any TEAE
- Any TEAE related to study drug according to the investigator
- Any severe TEAE
- Any serious TEAE
- Any TEAE leading to discontinuation of study drug
- Any TEAE leading to death
- TEAEs of Special Interest (as defined in [Appendix B](#))
- All deaths

- Deaths occurring \leq 30 days after last dose of study drug
- Deaths occurring $>$ 30 days after last dose of study drug

In addition, an overview of AEs per 100 patient-years of study exposure will be presented for the AE categories defined above. The number of TEAEs reported, the total number of years of study drug exposure, and the TEAE rate per 100 patient-years will be presented. For the SA_A and SA_C populations, 95% CI will be provided for the treatment differences between each upadacitinib group and placebo group. The treatment difference and 95% CI will be adjusted by the study size of the Phase 2b Induction Study and Induction Studies described by Sui et al.⁷

9.2.3 Treatment-Emergent Adverse Events by SOC and/or PT

Treatment-emergent adverse events will be summarized by SOC and PT; by maximum relationship to study drug as assessed by the investigator (e.g., reasonable possibility or no reasonable possibility) and SOC and PT; by maximum severity and SOC and PT; and by subject number and SOC and PT. Specific adverse events will be counted once for each subject for calculating percentages, unless stated otherwise. In addition, if the same adverse event occurs multiple times within a subject, the highest severity and level of relationship to investigational product will be reported. The SOCs will be presented in alphabetical order, and the PTs will be presented in alphabetical order within each SOC.

For summary by maximum severity, if a subject has an AE with an unknown severity, then the subject will be counted in the severity category of unknown, even if the subject has another occurrence of the same event with a severity present. The only exception is if the subject has another occurrence of the same AE with the most extreme severity – severe. In this case, the subject will be counted under the severe category.

For summary by maximum relationship to study drug, if a subject has an AE with an unknown relationship, then the subject will be counted in the relationship category of "unknown," even if the subject has another occurrence of the same event with a relationship present. The only exception is if the subject has another occurrence of the

same AE with a relationship assessment of "Reasonable Possibility." In this case, the subject will be counted under the "Reasonable Possibility" category.

In addition, treatment-emergent adverse events will be summarized by PT and sorted by decreasing frequency for the upadacitinib overall.

9.2.4 Treatment-Emergent Adverse Events per Patient-Years of Exposure

Exposure-adjusted AEs per 100 patient-years will be provided, where AEs per 100 patient-years of exposure are defined as the number of AEs divided by the total exposure in 100 patient-years, i.e.,

$$100 * (\text{Number of TEAEs}) / (\text{Total Patient Years})$$

where total patient years is defined as the sum of the study drug exposure of all subjects, normalized by 365.25, and rounded to 1 decimal place. Note that one event per preferred term per day per subject will be counted in the calculation of the number of AEs (i.e., a preferred term will not be counted twice on the same day for the same subject).

The TEAE rates per 100 patient-years of exposure will be provided for each AE category in the AE overview summary (defined in Section 9.2.2) and for TEAE summary by SOC and PT.

